	
 To evaluate the reactogenicity of COVID-19 vaccines, when given as 1- or 2-dose vaccination regimens, in pregnant participants. 	
 Occurrence of solicited local and general adverse events (AE) that occur during a 7-day follow-up period after each vaccination (i.e., the day of vaccination and 6 subsequent days) Occurrence of unsolicited AEs that occur during a 30-day follow-up period after vaccination (i.e., the day of vaccination and 29 subsequent days)
Secondary (maternal)	
 To describe pregnancy outcomes in women who receive COVID-19 vaccine(s) during pregnancy. 	
 Pregnancy outcomes from Visit 1 up to 6 weeks after delivery. These include live birth with congenital anomalies, miscarriage, fetal death/stillbirth (antepartum or intrapartum), mode of delivery, elective/therapeutic termination.
	
 To evaluate safety in terms of SAEs and medically attended adverse events (MAAEs) in women who receive COVID-19 vaccine(s) during pregnancy. 	
 Occurrence of serious adverse events (SAEs), AEs leading to study withdrawal, and MAAEs from Visit 1 (Day 0) up to 6 weeks after delivery
	
 To evaluate safety in terms of AESI (including potential immune-mediated medical conditions (PIMMCs)) relevant to COVID-19, including possible vaccine-enhanced disease, in all women at any time after the first dose of a COVID-19 vaccine 	
 AESI from Visit 1 up to 6 weeks after delivery. These include but are not limited to maternal death, hypertensive disorders of pregnancy (gestational hypertension, pre-eclampsia, pre-eclampsia with severe features including eclampsia), antenatal bleeding (morbidly adherent placenta, placental abruption, caesarean scar pregnancy, uterine rupture), postpartum haemorrhage, fetal growth restriction, gestational diabetes mellitus, non-reassuring fetal status, pathways to preterm birth (premature preterm rupture of membranes, preterm labour, iatrogenic preterm birth), chorioamnionitis, oligohydramnios,

		polyhydramnios, gestational liver disease (intrahepatic cholestasis of pregnancy, acute fatty liver of pregnancy), maternal sepsis.

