3.2 Secondary objectives

Maternal

- To describe pregnancy outcomes in women who receive COVID-19 vaccine(s) during pregnancy.
- To evaluate safety in terms of SAEs and medically attended adverse events (MAAEs) in women who receive COVID-19 vaccines during pregnancy.
- To evaluate safety in terms of AESI (including potential immune-mediated medical conditions (PIMMCs)) relevant to COVID-19, including possible vaccine-enhanced disease, in all women at any time after the first dose of a COVID-19 vaccine.
- To evaluate the immunogenicity of COVID-19 vaccines, when given as 1- or 2-dose vaccination regimens, in serologically negative (to SARS-CoV-2) pregnant participants.
- To evaluate the immunogenicity of COVID-19 vaccines, when given as 1- or 2-dose vaccination regimens, in pregnant participants (regardless of serostatus as baseline).

Infant

- To evaluate the safety of infants born to women vaccinated with COVID-19 vaccine(s) up to 12 months after birth.
- To evaluate the transfer of SARS-CoV-2 specific antibodies from mothers vaccinated with COVID-19 vaccine(s), according to different regimens, to their infants at the time of delivery
- To evaluate the kinetics of SARS-CoV-2 specific maternal antibodies in infants born to mothers vaccinated with COVID-19 vaccine(s), up to 3 months after birth
- To assess the effect of gestational age at vaccination, interval between vaccination and delivery, maternal age, health status, vaccine type and schedule on immune responses and duration of immune responses in vaccinated women and on placental transfer and antibody kinetics in their infants

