3.5 Secondary endpoints/outcomes

Maternal

- Pregnancy outcomes from Visit 1 up to 6 weeks after delivery. These include live birth with congenital anomalies, miscarriage, fetal death/still birth (antepartum or intrapartum), mode of delivery, elective/therapeutic termination.
- Occurrence of serious adverse events (SAEs), AEs leading to study withdrawal, and MAAEs from Visit 1 (Day 0) up to 6 weeks / 6 months after delivery

- AEFI from Visit 1 up to 6 weeks after delivery. These include but are not limited to maternal death, hypertensive disorders of pregnancy (gestational hypertension, pre-eclampsia, pre-eclampsia with severe features including eclampsia), antenatal bleeding (morbidly adherent placenta, placental abruption, caesarean scar pregnancy, uterine rupture), postpartum haemorrhage, fetal growth restriction, gestational diabetes mellitus, non-reassuring fetal status, pathways to preterm birth (premature preterm rupture of membranes, preterm labour, iatrogenic preterm birth), chorioamnionitis, oligohydramnios, polyhydramnios, gestational liver disease (intrahepatic cholestasis of pregnancy, acute fatty liver of pregnancy), maternal sepsis.
- SARS-COV-2 IgG-specific antibody concentrations, (and neutralizing antibody titres and cellular immune responses in subsets) measured on blood samples collected from vaccinated maternal subjects at Day 0 (before vaccination), Day 28-42, Day 56-84, Day 84-112, Day 112-140, at delivery, between 4 weeks and 12 weeks, and at 12 months after delivery

Infant

- From birth through 6 weeks after birth, occurrences of SAEs, AEs leading to study withdrawal, and MAAEs
- Occurrence of neonatal AEs of special interest (up to 6 weeks after birth). These include but are not limited to small for gestational age, low birth weight including very low birth weight, neonatal encephalopathy, congenital microcephaly (postnatally or prenatally diagnosed), congenital anomalies (major external structural defects, internal structural defects, functional defects), neonatal death (in a preterm live birth or in a term live birth), neonatal infections (blood stream infections, meningitis, respiratory infection), respiratory distress in the neonate, preterm birth, failure to thrive, large for gestational age, macrosomia
- Developmental status at 12 months of age

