3.6 Exploratory endpoints/outcomes

Maternal

- Levels of maternal IgA and/or other IgG (and subtypes) against SARS-CoV-2 in colostrum and breast milk within 3 days and 14 days where possible
- Occurrence of COVID-19 up to 12 months post-delivery
- SARS-COV-2 IgG-specific antibody concentrations, (and neutralizing antibody titres and cellular immune responses in subsets) measured on blood samples collected from vaccinated maternal subjects at Day 0 (before booster vaccination), Day 28-42, Day 56-84, Day 84-112, Day 112-140, at delivery, between 4 weeks and 12 weeks, and at 12 months after delivery
- SARS-COV-2 IgG-specific antibody concentrations, (and neutralizing antibody titres and cellular immune responses in subsets) measured on blood samples collected from vaccinated maternal subjects at Day 0 (before vaccination), Day 28-42, Day 56-84, Day 84-112, Day 112-140, at delivery, between 4 weeks and 12 weeks, and at 12 months after delivery

Infant

- Occurrence of COVID-19 up to 12 months post-delivery (infant)

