
 • To evaluate safety in terms of AEFI (including potential immune-mediated medical conditions (PIMMCs)) relevant to COVID-19, including possible vaccine-enhanced disease, in all women at any time after the first dose of a COVID-19 vaccine. 	
 • AEFI from Visit 1 up to 6 weeks after delivery (Day 42 post-delivery). These include but are not limited to maternal death, hypertensive disorders of pregnancy (gestational hypertension, pre-eclampsia, pre-eclampsia with severe features including eclampsia), antenatal bleeding (morbidly adherent placenta, placental abruption, caesarean scar pregnancy, uterine rupture), postpartum haemorrhage, fetal growth restriction, gestational diabetes mellitus, non-reassuring fetal status, pathways to preterm birth (premature preterm rupture of membranes, preterm labour, provider-initiated preterm birth), chorioamnionitis, oligohydramnios, polyhydramnios, gestational liver disease (intrahepatic cholestasis of pregnancy, acute fatty liver of pregnancy), maternal sepsis. 	
Notification of AEFI to site by participant from enrolment to 6 weeks after delivery for the mother and up to 6 weeks after birth for the infant.

 • To evaluate the immunogenicity of COVID-19 vaccines, when given as 1- or 2-dose vaccination regimens, in serologically negative (to SARS-CoV-2) pregnant participants. 	
 • SARS-CoV-2 IgG-specific antibody concentrations, (and neutralizing antibody titres and cellular immune responses in subsets) measured on blood samples collected from vaccinated maternal subjects at Day 0 (before vaccination), Day 28-42, Day 56-84, Day 84-112, Day 112-140, at delivery, between 4 weeks and 12 weeks, and at 12 months after delivery 	
Maternal blood sampling at Day 0 (before vaccination), Day 28-42, Day 56-84, Day 84-112, Day112-140, at delivery, between 4 weeks and 12 weeks, and at 12 months after delivery

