- Participants who are taking part in the breast milk sub-study will hand express a sample of colostrum from each breast. Participants will be provided with containers and instructions for the collection of subsequent samples
- Vital signs pre-vaccination
- **Vaccination with COVID-19 vaccine for those in cohort 3 (28 0/7 – 34 0/7 gestational weeks at recruitment)**
- Observation period post-vaccination for 20 minutes
- eDiary set up for those receiving a vaccine

Study visit 9 (postnatal)

12 - 16 days post delivery where possible at the participating institution for those in the breast milk sub-study group. All other participants can be reviewed at this visit by a telephone call.

- SAE / AESI / MAAE check
- Concomitant medication check
- Breast milk sample collection (at selected sites). Women will be asked to provide a sample of breast milk from each breast. This sample can be collected by the woman in advance and collected by a member of the research team if this is a remote visit.
- There will be further randomisation to determine whether the infant bloods are taken at 4-6 weeks after birth or at 10-12 weeks after birth except cohort 3 (cohort 3 will have infant and maternal blood samples taken at **28-42 days** post-delivery).
- eDiary check for those who received a vaccine post-delivery (cohort 3)

Study visit 10 (postnatal)

28-42 days OR 70-84 days post delivery at the participating institution / participant home (cohort 3 will have infant and maternal blood samples taken at 28-42 days post-delivery).

- SAE / AESI / MAAE check
- Concomitant medication check
- Targeted maternal physical examination if indicated
- Maternal immunogenicity blood sample collection
- Infant blood sample collection This will be a venous sample where possible, taken by an experienced member of the research team.
- eDiary check for those who received a vaccine post-delivery (cohort 3)

Study visit 11 (postnatal)

182 days (-/+ 14 days) post delivery review by telephone call.

- SAE / AESI / MAAE check
- Concomitant medication check

Study visit 12 (postnatal)

364 days (-/+ 14 days) post delivery at the participating institution / participant home.

- SAE / AESI / MAAE check
- Concomitant medication check
- Immunogenicity blood sample collection
- Infant examination and neurodevelopmental assessment – “Ages and Stages” Questionnaire if not already completed by a healthcare professional during routine care.

Contraindications to vaccination

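### The maternal AESI objective is open-ended from the first dose, but its endpoint and notification period close 6 weeks after delivery, while AESI checks run to 12 months

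*Protocol*

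**What the plan says.** **Objective.** The Trial Summary and sections 3.2 and 3.7 share one maternal safety objective. It covers AESIs and PIMMCs "relevant to COVID-19, including possible vaccine-enhanced disease, in all women at any time after the first dose of a COVID-19 vaccine".

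**Endpoint.** The Trial Summary gives the outcome as "AESI from Visit 1 up to 6 weeks after delivery". Section 3.5 has the same window under another label, "AEFI from Visit 1 up to 6 weeks after delivery". Section 3.7 repeats it with the day number added: "AEFI from Visit 1 up to 6 weeks after delivery (Day 42 post-delivery". The events named are obstetric, and the list is stated not to be exhaustive.

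**Notification.** The timepoint column of section 3.7 reads "Notification of AEFI to site by participant from enrolment to 6 weeks after delivery for the mother".

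**Visits.** Section 7 lists an "SAE / AESI / MAAE check" at Visit 11 (182 days after delivery) and Visit 12 (364 days), each within 14 days either way. The visit schedules in Appendix 4 show the same check at both visits for every cohort.

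**Neighbouring outcomes.** In the section 3.7 row for maternal SAEs and MAAEs, the outcome stops at 6 weeks but notification runs to 1 year after delivery. Section 3.5 gives two limits for that outcome, 6 weeks and 6 months, separated by a slash. The only maternal COVID-19 endpoint that runs to 12 months is exploratory: "Occurrence of COVID-19 up to 12 months post-delivery".

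**The concern.** An objective and its endpoint should cover the same period. Here the objective has no upper limit, the endpoint and notification period close at Day 42 after delivery, and the sites keep asking about AESIs until about Day 364. All four cannot be followed as written.

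Six weeks after delivery is a natural limit for the obstetric events listed. The same limit has been applied to PIMMCs and possible vaccine-enhanced disease, which the objective names without any limit. Enhanced disease presupposes an infection, and the trial tracks maternal infection to 12 months.

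What is at stake is the conclusion the endpoint can support. If it shows no such events, the objective's wording invites a statement about any time after the first dose, while the count behind it stops at Day 42. AESI information that sites have already solicited after that day would not enter the endpoint.

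**Working it through.** The protocol gives no figure for this, so there is none to reproduce. The check compares the four statements of the period and then measures the gap.

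**Side by side**

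| Element | Where | Ends |
|---|---|---|
| Objective | Trial Summary, 3.2, 3.7 | no limit after first dose |
| Endpoint | Trial Summary, 3.5, 3.7 | 6 weeks after delivery (Day 42 in 3.7) |
| Notification | 3.7 | 6 weeks after delivery |
| AESI checks | Section 7, Appendix 4 | Visit 12, Day 364 ± 14 |

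Six weeks and Day 42 agree with each other (6 × 7 = 42).

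**Postnatal gap.** 364 − 42 = 322 days. 322 / 364 = 88% of postnatal follow-up, or 46 weeks, lies outside the endpoint. This needs no assumption about gestation at birth.

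**Share of follow-up after dose 1.** Inputs are gestation at dose 1, *g*, between 13 and 34 weeks (section 6.1); endpoint end at 6 weeks after delivery; and follow-up end at 52 weeks after delivery. The protocol gives no gestation at birth, so 40 weeks is assumed.

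Coverage = ((40 − g) + 6) / ((40 − g) + 52)

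- g = 13: (27 + 6) / (27 + 52) = 33/79 = 42%
- g = 24: (16 + 6) / (16 + 52) = 22/68 = 32%
- g = 34: (6 + 6) / (6 + 52) = 12/58 = 21%

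The excluded shares are 58%, 68% and 79%.

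**Sensitivity to the assumed birth week.** Each week's change adds or removes one week from both numerator and denominator. Birth at 38 weeks gives 31/77 = 40% (g = 13) and 10/56 = 18% (g = 34). Birth at 42 weeks gives 35/81 = 43% and 14/60 = 23%. The 46 excluded weeks do not change.

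These shares apply to Cohorts 1 to 3, whose first dose is at Visit 1. Cohort 4 women had their first dose before enrolment.

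**Cohort 3, second dose.** If it is given at Visit 8, 0 to 7 days after delivery, the endpoint time left after it is 42 − 7 = 35 to 42 − 0 = 42 days.

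**Fit with the visits.** Outside Cohort 3, Visit 10 falls at 28–42 or at 70–84 days after delivery. For women in the later group, the last AESI check inside the window is Visit 9 (days 12–16), and the next falls after Day 42. That check could look back, but section 3.7 does not place one at the cut-off for this outcome.

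**The case against.** The strongest reply is that late cases are not lost, and this largely stands. Section 9.3 collects SAEs for the whole study and maternal MAAEs at any time, and section 9.8 repeats the latter. Section 10.3.3 presents SAEs with no 6-week cut. The data safety monitoring board reviews related SAEs and AESIs without a time limit (committee roles; Appendix 1), and Appendix 5 puts all SAEs and AESIs into the annual safety update report. An enhanced case needing admission is an SAE by definition (section 9.1). A reader might infer that enhanced disease after week 6 would go unrecorded or unreported; the protocol does not support that. None of these routes, however, is the endpoint for this objective, and the SAE/MAAE endpoint is itself written to 6 weeks in the Trial Summary and section 3.7.

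Three other inferences should be resisted:

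- **That the window misses the period of greatest risk**, because enhanced disease would emerge as antibody falls or immune-mediated conditions appear late. The protocol says neither. The present window does cover 12 to 33 weeks after dose 1, when infection can occur.
- **That 58–79% of events would be missed.** The percentages are shares of calendar time. The protocol gives no infection or AESI rate from which to estimate events.
- **That a table of severe maternal COVID-19 would close the gap.** Section 7 says maternal infections will be noted and a symptom diary given; it describes a clinical review visit for symptomatic infants and gives no maternal severity definition. Every woman is also vaccinated, so a longer window alone would not distinguish enhanced from ordinary severe disease.

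**Conclusion.** The mismatch holds. The objective has no end date, its endpoint and notification period stop at Day 42 after delivery, and AESI checks continue to about Day 364. The endpoint therefore leaves out the last 46 weeks of maternal follow-up. With birth at 40 weeks it covers 42% of the time after dose 1 for vaccination at 13 weeks and 21% for vaccination at 34 weeks.

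The consequence is limited to what this secondary, descriptive endpoint can support. It is not a failure to collect or report late safety events, and it does not touch the primary analysis. Nor is it a detail left to a statistical analysis plan: the protocol fixes the window, and fixes it against its own objective. It should be corrected. The finding rests on the text alone; only the percentages of follow-up depend on the assumed week of birth.

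**What to change.** Reconcile the objective, endpoint, notification period and visit schedule in the Trial Summary and sections 3.2, 3.5 and 3.7. Either route below resolves the point:

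1. **Split the endpoint.** Keep the listed obstetric AESIs from Visit 1 to 6 weeks after delivery. Count PIMMCs and possible vaccine-enhanced disease from Visit 1 to 12 months after delivery, using the AESI checks already scheduled at Visits 10 to 12, and change the notification cell in section 3.7 to match.
2. **Narrow the objective.** If the short window is intended, end the objective at 6 weeks after delivery and limit the conclusion to that period.

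In the same edit, use one label throughout (the Trial Summary says AESI; sections 3.5 and 3.7 say AEFI). Also settle the maternal SAE/MAAE window, now 6 weeks in two places and two alternatives in section 3.5.

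The cost is wording and, under the first route, one extra descriptive tabulation. No visit or procedure is added. The change concerns what is counted and reported, not how participants are managed.

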4 TRIAL DESIGN

This is a Phase II, multi-centre, randomised, single-blind, platform study evaluating the safety, reactogenicity and immunogenicity of COVID-19 vaccines in pregnant women participants in the UK.

The design is “adaptive” in that new COVID-19 vaccines may be included as soon as they are approved, and new schedules may be assessed as they become relevant or considered for implementation (e.g., one dose schedules in which the single dose is given earlier than 28 weeks’ gestation, etc).

Potential participants will be recruited through academic and NIHR clinical trials sites.

After signing informed consent, participants may be screened and enrolled. During the screening period nose/throat samples may be taken to detect SARS-CoV-2 by PCR, if the participant has any COVID-19 symptoms or significant exposure history.

Approximately 800 pregnant participants are planned for the study, but this will be dictated by the number of vaccines being evaluated. An effort will be made to enrol groups that are most affected by COVID-19, including ethnic minorities.

As determined by their gestation at recruitment (and whether they had already received a single dose of COVID-19 vaccine pre-pregnancy), participants will then be randomised to receive 1 or 2 intramuscular (IM) injections of either vaccine A or B or C (etc.), at one of two dosing intervals (see tables 1- 4).

5 TRIAL SETTING

This is a multicentre study which will take place across approximately 15 sites in the UK.

It is possible that further sites will be opened. If this occurs these sites will be added to the protocol at the next protocol update, and this will not alone necessitate a protocol amendment.

Women may receive information about the study from community midwives under the management of a trial site, through the national NIHR vaccine registry or through national or local advertising.

6 PARTICIPANT ELIGIBILITY CRITERIA

6.1 Inclusion criteria (maternal)

- Healthy women, or women with stable underlying medical conditions, 18 - 45 years of age, between 13 0/7 and 34 0/7 weeks' gestation on the day of planned vaccination, with an uncomplicated, singleton pregnancy, and who are at no known increased risk of severe COVID-19 or obstetric complications
- Able and willing (in the investigator's opinion) to comply with all study requirements
- Willing to allow the investigators to discuss the volunteer's medical history with their General Practitioner and access all medical records when relevant to study procedures
- Willing and able to give informed consent prior to study enrolment
- No contraindication to the specific vaccine to be administered in the study, according to the Green Book.

6.2 Exclusion criteria (maternal)

- Previous microbiological (based on a positive SARS-CoV-2 NAAT result) diagnosis of COVID-19
- Administration of immunoglobulins and/or any blood products within the 3 months preceding the planned administration of the study vaccine candidate (with the exception of anti-D immunoglobulin)
- Previous vaccination with any COVID-19 vaccine (main cohort); prior receipt of one dose of a COVID-19 vaccine is permitted (sub-study)
- Any confirmed or suspected immunosuppressive or immunodeficient state; chronic administration (defined as more than 14 continuous days) of immunosuppressant medication within the past 3 months, except topical steroids or short-term oral steroids (course lasting \leq 14 days).
- Any contraindication to the specific vaccine to be administered in the study, according to the Green Book or to the Summary of Product Characteristics for a specific vaccine.
- Current major illness of the mother or conditions of the fetus that, in the investigator's judgment, will substantially increase the risk associated with the participant's participation in, and completion of, the study or could preclude the evaluation of the participant's response, including but not limited to the following:
 - Uncontrolled gestational hypertension

- Preeclampsia-eclampsia
- Placental abnormality
- Polyhydramnios or oligohydramnios
- Significant bleeding or blood clotting disorder
- Uncontrolled gestational diabetes
- Any signs of premature labor with the current pregnancy or having ongoing intervention (medical/surgical) in the current pregnancy to prevent preterm birth
- Prior stillbirth or neonatal death, preterm delivery (≤ 34 weeks), or previous infant with a known genetic disorder or major congenital anomaly.

